15.1 Number of times in the past 12 months asthma symptoms required an emergency department or urgent care visit (but not an overnight stay in the hospital):						
	ER/urgent care visits (with no overnight hospital stay)	 None				
15.2 Number of times in the past 12 months that there was a worsening in asthma symptoms that required a hospital stay for greater than 24 hours:						
	times admitted to hospital	 None				
15.3 Number of unplanned ambulatory clinic visits due to exacerbation in past 12 months :						
	unplanned visit—Please list dates of the most recent unplanned ambulatory clinic visit below (DD-MMM-YYYY)					
a.						 None
b.						
c.						
d.						
e.						
f.						
15.4 How many courses of oral corticosteroids (OCS) was the patient prescribed over the past 12 months for asthma exacerbations unrelated to emergency department, urgent care or, unplanned ambulatory clinic visits or hospitalizations?						
 0 OCS courses for asthma within 12 months						
 1 OCS course only for asthma within the past 12 months						
 2 OCS courses only for asthma within the past 12 months						
 3 OCS courses for asthma within the past 12 months						
 ≥ 4 OCS courses for asthma within the past 12 months						
 patient is on daily OCS						

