An asthma exacerbation is defined by a change in asthma control requiring a course of oral steroids (i.e., at least 3 days with at least 10 days between each burst) and/or steroid injection and/or a hospitalization for asthma or emergency department visit for an asthma exacerbation. Importantly, record only the highest utilization for each exacerbation, do not double count exacerbation episodes. If an OCS course was due to a hospitalization, do not record as OCS course but as the hospitalization		
8.1	Number of times since the last visit that asthma symptoms required an emergency department or urgent care visit (but not an overnight stay in the hospital):	
	 ER/urgent care visits (with no overnight hospital stay)	 None
8.2	Number of times since the last visit that there was a worsening in asthma symptoms that required a hospital stay for greater than 24 hours:	
	 times admitted to hospital	 None
8.3	Number of unplanned ambulatory clinic visits due to exacerbation since the last visit:	
	 unplanned visit—Please list dates of the most recent unplanned ambulatory clinic visit below (DD-MMM-YYYY)	
a.		 None
b.		
c.		
d.		
e.		
8.4	How many courses of oral corticosteroids (OCS) was the patient prescribed since the last study visit for asthma exacerbations unrelated to emergency department, urgent care or, unplanned ambulatory clinic visits or hospitalizations?	
	 0 OCS courses for asthma  1 OCS course only for asthma  2 OCS courses only for asthma  3 OCS courses for asthma  ≥ 4 OCS courses for asthma  patient is on daily OCS	
8.5	Date of most current exacerbation:	   MMM     YYYY  unknown

Investigator/Coordinator Signature: _____

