Appendix B. Revisions to Select Analyses Initially Detailed in this SAP

Due to the nature of the data collected or to enhance clarity of presentation or interpretation of findings, some revisions were made to select analyses initially specified in the SAP. These revisions are detailed below:

- Novel site results were displayed in separate tables (N table series)
- All analyses by language were not conducted since the AIRQ was only administered in English language.
- There was no data on PRECISION education resource views/downloads for the specialty care cluster so tables 22c and 23c could not be run
- Some analyses could not be conducted due to the small sample size, e.g., for Tables 23e-23j, Tables 29b1-b3, Tables 29e-t, Table 30a, Table N4d, Tables N6b-N6i, Tables N7b-N7i, Table N8e, N10d, N22f, N23e, N29e-N29t or due to lack of data (i.e., no telehealth visits **CCI** or medical record history data available for the novel site so Table N3c, N4b, N4c, N5, N8d, N9b, N10b, N10c, N22e, N23e could not be presented).
- There was only one follow-up visit per patient so some analyses could not be presented (Table 24 and Table N24 series) or were modified (Table 25)
- Some tables duplicated content from other tables and are not presented (content for the Table 26, 27, N26 and N27 series can be found in the Table 20, 21, N20 and N21 series)
- Inferential statistical tests (e.g., ANOVA, chi-square test) were run to determine if differences between the practice clusters were statistically significant for Table 3e and Tables 8 series, Tables 10 series, Table 20 series
- A Bowker's test was used instead of a Cochran's Q test to evaluate if there were within-patient changes in OCS use (Table 31b) as the Cochran's Q test was not suitable 9 (only provides a method for testing three or more binary matched pairs).

Statistical analysis plan
D2287L00028 (EVA-26645)

AstraZeneca
27 Sep 2023

SIGNATURES

ASTRAZENECA SIGNATURES

D2287L00028 PRECISION Study 4 – Implementation

Statistical Analysis Plan for the Implementation of the US PRECISION AIRQ®,
Asthma Checklist, and Educational Resources (PRECISION Program) into
Clinical Practice Using Telehealth and In-Person Platforms: Addendum

This statistical analysis plan addendum has been subjected to an internal AstraZeneca review.

I agree to the terms of this statistical analysis plan.

AstraZeneca Study Statistician

PPD

Evidera Statistical Oversight

PPD

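### Table 31b tests within-patient change in OCS use with Bowker's test, which ignores category order; add a labelled post hoc ordinal test and an estimate of change

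*SAP*

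**What the plan says.** SAP Appendix B lists departures from the planned analyses. For Table 31b it states: "A Bowker's test was used instead of a Cochran's Q test to evaluate if there were within-patient changes in OCS use". The reason given is that Cochran's Q "only provides a method for testing three or more binary matched pairs". That explains dropping Cochran's Q. It does not explain choosing a nominal rather than an ordinal paired test.

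The Clinical CRF (Protocol Appendix I, item 15.4) asks "How many courses of oral corticosteroids (OCS) was the patient prescribed over the" past 12 months. The options run from "0 OCS courses for asthma within 12 months" through 1, 2 and 3 to "≥ 4 OCS courses for asthma within the past 12 months", with a sixth option, "patient is on daily OCS". The 12-month post-visit form (Protocol Appendix J, item 8.4) has the same ladder, ending in "≥ 4 OCS courses for asthma" and daily OCS. Protocol section 6.1.2 says the post-visit exacerbation data will be compared with the 12 months before the initial visit.

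The readable text does not give the categories of Table 31b, the number of pairs, the significance level or the handling of daily OCS. The exploratory sections where the table would be defined (SAP 4.2.3 and 5.1.3) are redacted.

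**The concern.** The pre/post comparison asks whether patients needed fewer OCS courses after the initial visit. That is a question about movement along an ordered scale. Bowker's test asks something broader: whether the paired table is symmetric in any respect. With several categories it spreads a consistent downward shift over many degrees of freedom, and many of the cells will be nearly empty.

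Two things are at stake. A real reduction could be reported as no significant change. And a significant result would not, by itself, tell the reader whether OCS use fell or rose, or by how much.

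**Working it through.** **Is there a figure to reproduce?** No. The documents give no sample size, OCS rate, effect or power for this table. The figures below are therefore conditional on stated assumptions.

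**Step 1: how many categories.** On two categories Bowker's test is McNemar's test. Naming Bowker makes more than two levels the likely reading, and the CRF item supplies five ordered levels plus daily OCS. This is an inference.

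**Step 2: what the statistic uses.** With n_ij the number of patients in category i before and j after,

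B = sum over i<j of (n_ij − n_ji)² / (n_ij + n_ji), on k(k−1)/2 degrees of freedom.

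Relabelling the categories leaves B unchanged, so order plays no part. Exchanging before and after changes only the sign inside the square, so a fall and an equal rise give the same B. Degrees of freedom are 5×4/2 = 10 for five levels and 6×5/2 = 15 with daily OCS as a sixth.

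**Step 3: analytic cost of the extra degrees of freedom.** A 1-df test with 80% power at two-sided 5% has non-centrality 7.85. At that same non-centrality, power is 65% on 3 df (critical value 7.81), 43% on 10 df (18.31) and 36% on 15 df (25.0).

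**Step 4: simulation on the CRF scale.** Assumptions: paired gamma-Poisson counts with a shared patient effect (shape 1), capped at 4; 30% reduction; two-sided 5%; Bowker's degrees of freedom counted on non-empty pairs only, which favours Bowker.

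| Courses per year before | Pairs | Bowker | Signed-rank |
|---|---|---|---|
| 1.0 | 100 | 13% | 57% |
| 1.0 | 150 | 27% | 75% |
| 1.0 | 250 | 57% | 93% |
| 0.5 | 100 | 8% | 36% |
| 0.5 | 200 | 19% | 61% |
| 0.5 | 300 | 35% | 78% |
| 0.3 | 100 | 8% | 25% |
| 0.3 | 250 | 17% | 49% |

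A repeat of 3,000 runs at 0.3 gave 7% against 22% and 20% against 50%, so those rows are good to about 3 points. The low rate matters because items 15.4 and 8.4 count only courses not linked to an emergency, urgent care, unplanned clinic or hospital episode. Under no change at 1.0 course, Bowker rejects about 2 to 4% of the time, so it is also conservative in sparse tables.

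**Step 5: where the gap shrinks, vanishes or reverses.**

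- Daily OCS as a sixth, highest level (assumed 5% of patients before, 30% of whom come off it), 1.0 course: 12% against 68% at 100 pairs and 45% against 92% at 200.
- Three levels (0, 1, 2 or more), 1.0 course, 150 pairs: 46 to 49% against 64 to 66% over repeated runs.
- Two levels: identical power (32% for both at 100 pairs, 1.0 course).
- 50% reduction from 0.5 course, 300 pairs, five levels: 95% against 100%.
- A change without a net shift (some patients better, others much worse), 200 pairs: Bowker 100%, signed-rank 34%.

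**The case against.** The strongest reply is that the criticism depends on a table nobody outside the sponsor can see. Appendix B speaks of OCS use, not OCS courses. The exacerbation dataset in SAP section 3 refers to EMR or claims data, and the CRFs also record chronic oral steroid therapy separately. The test first planned was for binary data, which fits a yes/no variable. A companion table may already hold an ordinal analysis or estimates. All of this stands, and it is why the power comparison must be conditional on the CRF levels.

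A reader might infer that Bowker's test is the wrong test or gives an invalid result. The documents do not support that: it is a recognised test for two paired multi-category measurements, and the substitution is disclosed. A reader might also infer that it always has only a fraction of the signed-rank power. That does not follow either, because the ratio depends on the number of levels, sample size, rate, effect and pattern of change, and Bowker can win.

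It is fair to add that direction can be read from the off-diagonal counts if the cross-tabulation is shown; the SAP already uses shift tables for AIRQ control level. That softens the point about direction but does not supply an estimate with a confidence interval.

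Two cautions apply to the remedy. The analysis is reported as done, so swapping in a more powerful test now would be post hoc test selection. And dropping every patient on daily OCS at either time would condition on a post-visit state and remove the clearest worsening and improvement. Both are met by adding rather than replacing, and by keeping those patients in the main run.

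**Conclusion.** The point holds in conditional form. Bowker's test is valid here, but it ignores order and its result carries no direction or size; that follows from the formula. If Table 31b uses the five ordered CRF levels, then under an assumed 30% net reduction with 100 to 250 pairs its power relative to the signed-rank test runs from about 13/57 = 0.23 to 57/93 = 0.61 at 1.0 course per year, and from about 8/25 = 0.32 to 17/49 = 0.35 at 0.3.

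These sizes rest on assumed rates, effect, dispersion, significance level and number of pairs. A modest number of pairs is plausible: they come only from patients who consented again at selected sites, and Appendix B says several other tables could not be run for small numbers. The count for Table 31b is nevertheless not given.

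Within-patient OCS change is not among the primary or secondary objectives, and the study is described as descriptive. The consequence is a less informative supporting result, not a threat to the main conclusions.

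**What to change.** 1. State in Appendix B the categories of Table 31b, the number of pairs and how daily OCS was handled.
2. Keep Bowker's result as reported.
3. Add, labelled post hoc, a Wilcoxon signed-rank test (or a marginal shift test) on the ordered categories.
4. Give the numbers decreasing, unchanged and increasing, with a 95% CI for D = p_dec − p_inc. A large-sample standard error is √{[p_dec + p_inc − (p_dec − p_inc)²]/n}. Do not rely on a mean of counts top-coded at 4 or more.
5. Show transitions to and from daily OCS explicitly. Rank daily OCS highest in the main run and exclude those patients in a sensitivity run.
6. If the table is binary, use exact McNemar with the difference in proportions instead of items 3 and 4.

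The cost is a short addition to Appendix B and one re-run on data already collected. The downside is one extra post hoc exploratory test, in a plan that makes no multiplicity adjustment (SAP section 6.2), so it should be read as descriptive support.
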